#### **2.4.6.6 Sample Size**

A consensus sample would be optimal in this feasibility study (all patients meeting criteria consented and participated), however since that is unlikely, a convenience sample will be used. The future of patients with COVID-19 disease requiring ICU admission is uncertain. A conservative estimate of 50% of these patients will develop PICS. In the first month at BJH, 29 patients were discharged from the ICU. This translates into approximately 15 patients per month. Although this number may increase or decrease due to uncertainties surrounding the disease. Previous studies (see literature review) suggest care for PICS should begin within 12 weeks of discharge. Therefore once IRB approval is obtained, patients discharged within the past 10 weeks will be screened for possible participation. A post-hoc power analysis will be done.

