## 1. SYNOPSIS

[figure not shown]
Study Title	COVID-19 Virtual Post Intensive Care Syndrome (CoV-PICS) Clinic: Modern, Convenient and Practical Recovery Care.
Objective	To determine if discharged COVID-19 patients with PICS symptoms are willing and able to navigate the technology necessary to participate in a virtual outpatient clinic (feasibility and acceptance). To determine if a multidisciplinary group of professionals, familiar with PICS, are able to interpret information obtained from virtual visits and patient self-reported surveys to make recommendations for future care based on baseline and changes in patient symptoms over time (feasibility). To determine the ease of receiving and receptiveness of primary care physicians to a summary of clinic recommendations (feasibility and acceptance). To determine if the PICS symptoms and patient characteristics of patients with an ICU stay due to COVID-19 are similar to those reported in the literature of non-COVID-19 patients.
Study Period	Planned enrollment duration: Aug 2020 – Feb 2021  Planned study duration: Aug 2020 – Aug 2021
Number of Patients	80, adult (minimum age 18, no maximum)
Study Treatment	None
Study Design	Observational feasibility trial
Inclusion and Exclusion Criteria	
Inclusion Criteria:
 
 
1. Patients who are at least 18 years of age
 
2. COVID-19 diagnosis with a stay in the intensive care unit at BJH
 
3. Missouri resident
 
 
Exclusion Criteria:
 
 
1. Severe cognitive deficits or dementia prior to hospitalization
 
2. Long-term resident of a skilled nursing facility prior to admission
 
3. Non-English speaking (will not have an interpreter available)
 
4. Hospice or Comfort Care at discharge
 
5. No plans to return to some degree of independent living at the time of discharge
 
6. Pregnant or a prisoner at the time of discharge
 
7. Blind or deaf
 

CONFIDENTIAL: This document is the intellectual property of [name]. Acceptance of this document constitutes the agreement by the recipient that no unpublished information contained herein will be published or disclosed without prior written approval.

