Statistical Methodology	
Descriptive statistics will be used to summarize the data. Continuous variables will be reported as medians and interquartile ranges or means and standard deviations as appropriate. Categorical variables will be reported as frequencies and percentages. Changes in the scores or times of the ICU Memory Tool®, PROMIS®29 Profile, MOCA-5 minute, Katz and Lawton®, PG-SGA short form®, Five time sit-to-stand and Two-minute step test, from hospital discharge to 3- and 6-month post discharge will be estimated using the Wilcoxon Signed Rank Test (non-parametric alternative to t-test) and compared across different categorical variables (e.g. age, gender, discharged directly to home, 30-day readmission) using ANOVA and continuous variables (e.g. APACHE IV, ICU length of stay) using ANCOVA.
 
A consensus sample would be optimal in this feasibility study (all patients meeting criteria consented and participated), however since that

CONFIDENTIAL: This document is the intellectual property of [name]. Acceptance of this document constitutes the agreement by the recipient that no unpublished information contained herein will be published or disclosed without prior written approval.

	
is unlikely, a convenience sample will be used. The future of patients with COVID-19 disease requiring ICU admission is uncertain. A conservative estimate of 50% of these patients will develop PICS. In the first month at BJH, 29 patients were discharged from the ICU. This translates into approximately 15 patients per month. Although this number may increase or decrease due to uncertainties surrounding the disease. Previous studies (see literature review) suggest care for PICS should begin within 12 weeks of discharge. Therefore once IRB approval is obtained, patients discharged within the past 10 weeks will be screened for possible participation. A post-hoc power analysis will be done.

--	---

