### **2.1.1 Preliminary Data**

Although some evidence exists regarding the characteristics of inpatients with COVID-19 disease, it is far from robust. In addition, it is not clear what staff to inpatient interactions, such as frequency of therapy sessions or inpatient nursing education, were forgone due to the risk of viral contamination and need to preserve personal protection equipment. A Washington University IRB approved (#202005039) observational study at BJH will add to the COVID-19 body of literature on these topics and some of the pertinent data obtained will be used in the interpretation of results of the proposed study herein. Evidence regarding long-term complications of COVID-19 disease is lacking, however insights from PICS may provide a roadmap for the future care of these patients. It is highly likely, COVID-19 patients will suffer from similar physical, cognitive and mental health issues long-term.

The physical impairments associated with PICS are believed to stem from ICU acquired weakness (ICU-AW) which is a combination of polyneuropathy, myopathy, neuromyopathy and muscle deconditioning. Patients with PICS are reported to have poor mobility, frequent falls and a dramatic loss of independence with activities of daily living (ADLs). A study by Borges et. al. compared 72 patients with sepsis/septic shock to a healthy control group. The patients admitted to the ICU had a substantial reduction in physical activity, exercise capacity and muscle strength at 3 months post discharge. An evaluation of 109 ARDS patients, demonstrated that although there was an improvement in the six-minute walk test at 12 months, the results were still only 66% of predicted distance and only 49% of the patients had returned to work. These findings were confirmed in another study which found 69% of patients with PICS were still restricted in performing ADLs and 50% had not returned to work 12 months after discharge.

In addition to long lasting physical detriments, new or worsening impairments in cognitive

CONFIDENTIAL: This document is the intellectual property of [name]. Acceptance of this document constitutes the agreement by the recipient that no unpublished information contained herein will be published or disclosed without prior written approval.

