### **3.3 Recruitment and Informed Consent**

Patients who are +COVID-19 with a stay in the ICU will be screened. A list of patients that meet these criteria that includes the patient's name and medical record number will be provided by the PI for (IRB#202005039) study: "The Effects of COVID-19 on Nursing Indicators, Delirium, Nutritional Status and Functional Mobility" (see attached letter). The research coordinator will review the medical record for exclusion criteria, if none exist, and a contact phone number is available, the research coordinator will complete a phone screen (see attached). The research coordinator will call in the patient from a private room. If the phone screen demonstrates the patient has potential signs and symptoms of PICS and the mental capacity to answer questions, a verbal consent will be sought (see attached). Prior to consent the patient will be asked if they need to move to a private area or if the prefer to invite family members to present. Verbal consent is being sought as the current study does not include any patient intervention.

CONFIDENTIAL: This document is the intellectual property of [name]. Acceptance of this document constitutes the agreement by the recipient that no unpublished information contained herein will be published or disclosed without prior written approval.

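### Expected refusal does not justify a convenience sample: the listed patients can be approached consecutively, and without that or a log of non-enrolment, willingness has no denominator

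*Combined protocol and SAP*

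**What the plan says.** Section 2.4.6.6 describes the best case as one in which "all patients meeting criteria consented and participated". It calls this a consensus sample, apparently meaning a census or consecutive sample. It then says "however since that is unlikely, a convenience sample will be used". The Statistical Methodology row of the Synopsis repeats this ("is unlikely, a convenience sample will be used"). Neither place gives another reason.

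Sections 2.3 and 3.3 describe how patients are found. The investigator of a companion study supplies "A list of patients that meet these criteria", with name and record number, the criteria being a positive COVID-19 status and an ICU stay. The coordinator reviews each record. If there is no exclusion and a phone number is available, the coordinator completes a phone screen. Consent is sought if the screen suggests PICS symptoms and the patient can answer questions. Section 2.4.6.6 adds that patients discharged in the previous 10 weeks will be screened once approval is given.

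The planned number is "80, adult (minimum age 18, no maximum"), over "Planned enrollment duration: Aug 2020 – Feb 2021".

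In section 2.4.1 the enrolment log entry is made on Day 1, alongside the documentation of consent. Patients who do not complete the first surveys and do not answer calls are classed as enrolment failures. Section 2.4.2, on minimising bias, has one sentence, about gender and ethnic background.

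**The concern.** The stated reason concerns who will agree. The choice it is used to support concerns who will be asked. Non-consent is a reason to record and report refusals. It is not a reason to give up approaching everyone, and the label sits badly beside a procedure that works through a list.

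The Synopsis and section 2.4 ask whether discharged patients with PICS symptoms are willing to use a virtual clinic and can manage its technology. Willingness is a proportion: those who agreed, out of the eligible patients approached. The primary outcomes in section 2.4.6.3 contain no such proportion, and no log is described from which to build one.

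The other primary outcomes are exposed as well. A patient who answers a recruitment call readily is plausibly also more likely to attend, arrive on time and complete online questionnaires. If contact order or persistence is left to convenience, those outcomes could be overstated, and a reader of the results could not tell by how much.

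**Working it through.** **1. The logic, side by side.**
- Section 2.4.6.6: full consent and participation is unlikely, therefore a convenience sample.
- Sections 2.3 and 3.3: a list is supplied, each record is reviewed, and those with no exclusion and a phone number are screened by phone.
- The second procedure can be carried out whatever the consent rate, so the first inference does not follow.

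**2. The plan's own figure.** Section 2.4.6.6 states "In the first month at BJH, 29 patients were discharged from the ICU" and assumes 50% develop PICS: 29 × 0.50 = 14.5, which reproduces the stated rate of about 15 per month. The target of 80 has no stated derivation.

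**3. The expected pool.** Assume a constant 15 per month, an enrolment window of 6 to 7 months, and the same rate during the look-back. Ten weeks at 4.348 weeks per month is 2.30 months.

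| Window | Pool without look-back | 80 as share | Pool with look-back | 80 as share |
|---|---|---|---|---|
| 6 months | 15 × 6 = 90 | 89% | 15 × 8.30 = 124.5 | 64% |
| 7 months | 15 × 7 = 105 | 76% | 15 × 9.30 = 139.5 | 57% |

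These pools are before the exclusions in section 2.3.2, so the eligible pool is smaller and the shares larger.

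**4. Does the order of approach matter?** Only if 80 is reached before the list is exhausted. Section 2.1.1 cites 20–50% of symptomatic patients seeking care at PICS clinics. If uptake here were similar (an assumption, since this is a virtual clinic), enrolment with the look-back would run from 0.20 × 124.5 = 25 to 0.50 × 139.5 = 70. The target would not be reached and order would have no effect on who enrols. Call persistence and non-response would still matter.

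**5. The opening of enrolment.** At 29 discharges per month, the look-back brings in 29 × 2.30 = about 67 patients at once, about 33 of them with PICS at 50%. The same section says care should begin within 12 weeks, so the earliest discharged have about 12 − 10 = 2 weeks left. Someone must decide whom to call first, and the available text does not say how.

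**6. What the unobserved share can do.** This is an illustration, not an estimate of bias. Assume 64 of 80 enrolled patients (80%) meet some feasibility criterion. The 95% Wilson interval is 70–87%. If nothing is known about the rest of the pool, feasibility in the whole pool lies between f × 0.80 and f × 0.80 + (1 − f), where f is the enrolled share:
- f = 0.573: 0.46 to 0.89
- f = 0.643: 0.51 to 0.87

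The lower limits fall well below the Wilson limit of 70%. Unreported non-enrolment can therefore matter more than sampling error.

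**7. The denominator.** No outcome or analysis in sections 2.4.6.3 to 2.4.6.5 counts patients listed, eligible, reached, refusing or consenting. The log described in section 2.4.1 begins with consented patients.

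**The case against.** The strongest reply is that the procedure is already close to consecutive. Read literally, sections 2.3 and 3.3 screen every listed patient who has no exclusion and has a phone number, and no step selects by ease of contact. On this reading the word convenience merely labels whoever agrees. Much of this stands. A reader might infer that feasibility will be estimated in the patients easiest to reach, but the documents support that only as a risk. The shares in the working also leave limited room for picking. Against this, section 2.4.6.6 still names the method as convenience, and nothing visible fixes the order or the number of calls.

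A reader might also infer that the coordinator holds a full list of ICU survivors. The documents do not call the list complete, nor do they limit it to survivors.

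It is tempting to put a number on the bias. Suppose 139 candidates, of whom half are easy to reach (80% would attend) and half hard to reach (50%), so the true figure is 65%. Taking 70 easy patients first gives (70 × 0.80 + 10 × 0.50)/80 = 76%, an 11-point excess. That figure does not stand as an estimate. The split has no source in the documents, and it needs every easy patient to enrol, which contradicts the expectation of incomplete consent. Under consecutive approach, with 80% of the easy half and 35% of the hard half enrolling (also assumed), the result is (56 × 0.80 + 24 × 0.50)/80 = 71%, still 6 points too high. A change of sampling method cannot remove differential consent.

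Finally, the phone screen and the letter about the list are attachments that are not in the documents reviewed. Contact rules may be there. If so, they should be brought into the protocol text.

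**Conclusion.** The point holds as a flaw of design and reporting. The only reason given for convenience sampling does not support it, and the label conflicts with the plan's own list-based screening. With no visible approach order or call rule, a log that begins at consent, and baseline non-responders set aside as enrolment failures, the enrolled group may be easier to reach and more willing than the eligible group. Attendance, on-time arrival and survey completion may be overstated, and the willingness part of the objective cannot be estimated.

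The direction is plausible but unproven, and the size cannot be derived from the documents. The 36–43% unobserved share rests on a constant 15 per month, a 6 to 7 month window, the look-back at the same rate, and 80 patients being enrolled. The 46–89% and 51–87% ranges rest in addition on an assumed 80% among the enrolled. They show what could go unseen, not what will happen.

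**What to change.** - **Sampling.** In sections 2.3 and 2.4.6.6, and in the Synopsis, replace the convenience sample with consecutive approach: every listed patient who passes record review, in discharge-date order, with the same fixed number of call attempts, until enrolment closes.
- **Frame.** State whether the companion study's list is complete and, if not, who is missing.
- **Flow.** Keep a screening log from the first call. Report counts listed, eligible, reached, symptom-positive, consented and baseline-complete, with reasons for each loss. Count enrolment failures in this flow.
- **Uptake.** Add uptake among eligible patients approached, with a 95% confidence interval, as a feasibility outcome.
- **Comparison.** Compare enrolled patients with eligible non-enrolled patients. All ICU survivors would be the wrong reference, because that mixes the intended symptom, capacity and technology criteria with selection. Use whatever screening data or aggregate companion-study data the approvals allow. Section 2.1.1 says "some of the pertinent data obtained will be used in the interpretation of results of the proposed study herein", but it does not promise data on non-participants, and this study's chart review follows consent, so permission must be confirmed.

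The cost is a few sentences, more recruitment calls, a screening log and one table. The log is the urgent part, because counts of unreached and refusing patients may not be recoverable later. Differential consent and the phone, technology and capacity filters will remain and should be stated as limits on generalisation.

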Day 1-2  Week 10 post initial visit And Week 22 post initial visit	
RC: If patient not enrolled in MyChart or has forgotten how to access, call patient and walk them through obtaining access. Direct link (attached to the patient’s study ID) will be emailed or texted (per patient preference) to access the following surveys, requesting one week turn-around time:
 
ICU Memory Tool® (measures recall and aids in our understanding of quality of life)
 
PROMIS®29 Profile (measures anxiety, depression, fatigue, pain, physical function, sleep and ability to participate in social roles)
 
MOCA-5 minute® (measures cognitive function)
 
PG-SGA short form® (screens for malnutrition risk)

Day 2-9  Week 11 and Week 23 post initial visit	
RC: Will send form email from PI to PCP (if patient agreed to share information) providing an overview of the study (see attached)
 
RC will obtain notice from RedCap when surveys opened. RC will check completeness of survey responses. If surveys not completed within 5 days, send reminder email. If not completed in 7 days, call patient offering to administer surveys over the phone.

Day 11  Week 11 and Week 23 post initial visit	
RC: If patient does not complete surveys within 7 days of receipt and has not responded to phone calls; considered an enrollment fail (start of study) or withdrawal from study (repeat surveys), document on enrollment log.

Day 2-11  Week 11 and Week 23 post initial visit	
RC: If surveys completed, send thank you email. Email and/or call patient to schedule first virtual visit. Email link to research team members for them to review responses in RedCap.

Day 9 – 18  Week 12 and Week 24 post initial visit	
RC: Schedule initial 60-75 minute virtual assessment based on MD schedule. Email all team members to obtain availability in non-physician visit time. Send outlook calendar appointments to team members. All providers engaging in telehealth visits will be licensed in the state where the participant lives.

1-2 days before virtual team visit	
RC: Send reminder email to research team members who will be on the visit. Send agenda for call – member/time slot. Send instructions/link for team members to join the virtual visit. Email the patient the instructions on how to access the virtual appointment in MyChart or the HIPPA approved WashU ZOOM link.

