Week 25 - 26	RC: Send final surveys to patient via link. An email with a link will also be sent to their PCP – at the start of their survey a statement will be made clearly stating if they complete the survey they are consenting to the study. The final survey tools sent will include: FIM® (feasibility of intervention measure), IAM® (intervention appropriateness measure) and the AIM® (acceptance of intervention measure). If surveys not completed within 5 days, send reminder email. If not completed in 7 days, if patient – phone call offer to administer surveys over the phone; if PCP send 2 nd email reminder. If the PCP does not complete, will consider denial to participate (document on enrollment form).
Week 25 - 26	RC: Once final surveys are completed email patient informing them their participation in the study is now completed, thanking them for their time and offering any final comments regarding the feasibility of the clinic may be emailed.
RC: research coordinator, PI: principle investigator, PCP: primary care physician	

CONFIDENTIAL: This document is the intellectual property of [name]. Acceptance of this document constitutes the agreement by the recipient that no unpublished information contained herein will be published or disclosed without prior written approval.

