## **2.4.3 Pre-Study Period**

## **2.4.4 Study Period**

### **Methods:**

## **2.4.6 Observations and Measurements**

### **2.4.6.3 Primary Outcome Measures**

Primary outcomes:

1. Patient adherence and determination of feasibility and acceptance with the virtual clinic and telehealth visits based on the FIM® (feasibility of intervention measure), IAM® (intervention appropriateness measure) and the AIM® (acceptance of intervention measure)
2. Patient attendance record
3. Number of on-time arrivals to the virtual visit
4. Number of patient successfully completed online questionnaires after initial training.
5. Patient primary care or clinic physician feedback using the tools in #1 and open ended comments.

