### **2.4.6.5 Statistical Methods**

Descriptive statistics will be used to summarize the data. Continuous variables will be reported as medians and interquartile ranges or means and standard deviations as appropriate. Categorical variables will be reported as frequencies and percentages. Changes in the scores or times of the ICU Memory Tool®, PROMIS®29 Profile, MOCA-5 minute, Katz and Lawton®, PG-SGA short form®, Five time sit-to-stand and Two-minute step test, from hospital discharge to 3- and 6-month post discharge will be estimated using the Wilcoxon Signed Rank Test (non-parametric alternative to t-test) and compared across different categorical variables (e.g. age, gender, discharged directly to

CONFIDENTIAL: This document is the intellectual property of [name]. Acceptance of this document constitutes the agreement by the recipient that no unpublished information contained herein will be published or disclosed without prior written approval.

home, 30-day readmission) using ANOVA and continuous variables (e.g. APACHE IV, ICU length of stay) using ANCOVA.

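### The post-hoc power analysis is undefined and cannot inform the primary feasibility outcomes, which need stated precision, confidence intervals and a fixed denominator that keeps non-responders in

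*Combined protocol and SAP*

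**What the plan says.** The synopsis gives the number of patients as "80, adult (minimum age 18, no maximum". Section 2.4.6.6 (Sample Size) does not mention 80. It describes a convenience sample, an expected flow of about 15 candidates a month and a 10-week look-back, and closes with "A post-hoc power analysis will be done". The synopsis entry on statistical methodology ends with the same sentence.

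The primary outcomes in 2.4.6.3 include an attendance record, "Number of on-time arrivals to the virtual visit", "Number of patient successfully completed online questionnaires after initial training", the FIM, IAM and AIM ratings, and physician feedback. None has a hypothesis, threshold or denominator. For data of this kind, 2.4.6.5 says "Categorical variables will be reported as frequencies and percentages"; continuous variables get medians with interquartile ranges or means with standard deviations. The Wilcoxon test, ANOVA and ANCOVA in that section apply to changes in the instruments that 2.4.6.4 lists as secondary.

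Under 2.4.1, a patient who has not returned the surveys within 7 days and does not answer calls is "considered an enrollment fail (start of study) or withdrawal from study (repeat surveys" and is recorded on the enrolment log. Before that, the coordinator offers to give the surveys by phone. Section 2.5.2 also allows withdrawal for inactivity, on the investigator's decision or at the patient's request. At weeks 25–26, "The final survey tools sent will include: FIM® (feasibility of intervention measure", along with IAM and AIM; a primary care physician who does not reply is treated as declining to take part.

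**The concern.** A power analysis needs a test, an effect and an alpha, and the plan names none of them for this one. Power is not defined for the primary outcomes, because nothing is tested on them. If the analysis is run on observed effects, it re-expresses the p-value and can neither justify the sample nor explain a null result. What a feasibility study should plan is precision, and that is missing.

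The denominator matters more. A patient who stops answering surveys and calls is a patient for whom the virtual clinic did not work. Adherence and attendance are primary outcomes, yet the rules can take these patients out of the study before the later rounds are counted. The plan does not say whether they stay in the percentage. If that is settled after the data are seen, the headline feasibility result depends on the choice.

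**Working it through.** **The plan's own figures.** The target is 80 (synopsis). With no alpha, power, effect, standard deviation, threshold or interval width in the documents, no power or precision formula can be run to reproduce it. The only arithmetic in 2.4.6.6 is 29 discharges × 0.50 = 14.5, which agrees with its figure of about 15 a month. That describes patient flow and says nothing about precision.

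**Precision that 80 gives.** These are exact (Clopper-Pearson) 95% intervals; the 95% level and the observed proportions are my assumptions.

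- 40/80 = 50%: 38.6–61.4%, half-width 11.4 points
- 64/80 = 80%: 69.6–88.1%
- With fewer patients at 50%: 30/60 gives 36.8–63.2% (half-width 13.2 points) and 20/40 gives 33.8–66.2% (16.2 points)

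For a mean FIM, IAM or AIM score, the half-width is t(0.975, n−1)/√n in SD units: 1.990/√80 = 0.22 SD with 80 respondents and 1.998/√64 = 0.25 SD with 64.

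**What observed power would add.** With z_p the two-sided normal quantile for the p-value, observed power is 1 − Φ(1.96 − z_p) + Φ(−1.96 − z_p).

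- p = 0.05, z_p = 1.960: power 0.50
- p = 0.20, z_p = 1.282: power 0.25

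This is a normal approximation and not exact for the Wilcoxon test, ANOVA or ANCOVA. It shows that the figure is a function of the p-value alone. It applies only if observed effects are used.

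**Effect of the denominator.** The documents give no attrition figure, so the counts are assumed: 80 consented, 56 attending a later visit, and w non-attenders already withdrawn. The percentage among those remaining is inflated by the factor 80/(80 − w).

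| w | Among those remaining | Among all 80 | Factor |
|---|---|---|---|
| 8 | 56/72 = 78% | 56/80 = 70% | 1.11 |
| 16 | 56/64 = 88% | 70% | 1.25 |
| 24 | 56/56 = 100% | 70% | 1.43 |

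At w = 16 the exact intervals are 77–94% (56/64) and 59–80% (56/80). The shift is 87.5 − 70.0 = 17.5 points.

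**First survey round.** Patients who return no baseline survey and do not answer calls become enrolment fails. If they are left out, completion by any mode in that round is close to 100% by construction. Surveys given by phone raise a second question, because the primary outcome is online completion and 2.4.1 does not say how phone surveys count.

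**The case against.** The strongest reply is that the power sentence may refer only to the secondary tests in 2.4.6.5, perhaps as the effect detectable at the achieved sample size. It would then be unfair to fault it for not serving outcomes that it never claimed to serve, and defining it would be an alternative to deleting it. This stands in part. A reader might infer that observed power is planned; the documents do not say so, and that criticism is conditional. But even on the kinder reading the analysis is undefined, and the primary outcomes still have no planned precision.

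A second reply is that counts and percentages let any reader compute an interval, and that the enrolment log allows either denominator to be rebuilt. This is true for the investigators, and it is why the gap is not fatal. A reader of the published report cannot recover a denominator that is not declared.

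Three stronger readings are tempting and not supported:

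- That the study is underpowered or needs a power calculation. An observational feasibility study with a declared convenience sample does not need one.
- That the plan excludes withdrawn patients from percentages, or that doing so gives a falsely tight interval. The plan is silent on the first. On the second, the half-widths in the illustration are 8.8 and 10.5 points, and the intervals overlap; the problem is the shift in the estimate.
- That the accrual figures contradict the target of 80. Section 2.4.6.6 says that patient numbers may rise or fall, and no participation rate is given, so neither conflict nor agreement can be shown.

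**Conclusion.** The point holds and should be acted on, as a cheap improvement to a sound type of design. The power sentence has no defined content and cannot inform the primary outcomes. The primary outcomes have no planned intervals, and 80 is tied to no precision, although it would give about 11 points either side of 50%. The open denominator carries most of the weight: percentages among those remaining would overstate adherence and attendance, by 17.5 points in the main illustration. That size rests wholly on the assumed 16 withdrawals and 56 attenders, and on the withdrawn patients being non-attenders. The direction does not depend on those counts: once any non-attender is removed, the percentage rises.

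**What to change.** 1. Delete the post-hoc power sentence in 2.4.6.6 and in the synopsis. In its place, state the precision at the target: about 11 points either side of 50% at n = 80, wider if fewer enrol. Add that this covers sampling error only and not selection into a convenience sample.
2. Report attendance, on-time arrival and online questionnaire completion for each visit or survey round with exact 95% intervals. Use all consented patients as the denominator. Keep first-round enrolment fails and all later withdrawals (under 2.4.1 and 2.5.2) in it as not completed or not attended, and show deaths separately. Count surveys given by phone as not completed online and report their number separately. Report on-time arrival among attenders as well, so that punctuality is not merged with attendance.
3. Report FIM, IAM and AIM with 95% intervals, for patients and physicians separately, with the number responding out of the number sent.

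The cost is wording and slightly more reporting, with no extra patients, visits or data; the enrolment log already records fails and withdrawals. The downside is that the proportions and their precision may look less favourable.
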